**COVER PAGE**

**STATISTICAL ANALYSIS PLAN**

**OFFICIAL TITLE: PET Imaging Study of Amish and Mennonite Patients with *CNTNAP2* Mutations**

**NCT NUMBER: NCT02983058**

**DATE OF DOCUMENT: May 22, 2019**

## Statistical Analysis Plan

The study was designed to enroll 40 individuals (20 affected with the mutation and 20 unaffected) in a cross-sectional biomarker validation study comparing PET mGluR5 binding between *CNTNAP2* mutation carriers and their unaffected first-degree relatives.

*Specific Aim 1:* Validate PET mGluR5 binding as a downstream marker of mTOR kinase hyperactivity, using individuals with *CNTNAP2* as an “experiment of nature” to assess consequences of mTOR kinase-pathway mutations on PET mGluR5 binding.

Primary hypothesis: mGluR5 binding will differ in patients with *CNTNAP2* mutations compared with normal controls.

Two-sample t-tests will be used to test for the global effects of *CNTNAP2* mutation versus unaffected controls on mGluR5 PET ligand binding, with regional  $BP_{ND}$  in DLPFC as the primary outcome variable. Two-sided statistics will be used, to assess potential increases or decreases in mGluR5 PET binding, related to underlying alterations in mGluR5 expression.

Decay-corrected reconstructed PET images will be co-registered to the anatomical MRIs acquired at the beginning of the study, using maximization of mutual information as implemented in SPM8 software. ROIs will be drawn on the MRIs and transferred to the co-registered PET images. Included ROIs will be: HPC and prefrontal (dorso-lateral, medial and orbitofrontal) cortices (19,20), as well as associative, sensorimotor, and ventral subregions of the striatum, thalamus, and occipital, parietal, and temporal cortices. In addition, cerebellum will be included as a reference region to estimate the distribution volume of the non-displaceable compartment ( $V_{ND}$ ). Time activity curves will be generated from ROI data and subsequently fitted to a 2-tissue compartment model (2TC) with arterial plasma input. Total distribution volume ( $V_T$ ) will be computed in each region including cerebellum from the estimated rate constants. The binding potential relative to the non-displaceable compartment,  $BP_{ND}$ , will be computed indirectly as  $[V_T(ROI)/V_T(CER)] - 1$ .

*Specific Aim 2:* Evaluate PET mGluR5 binding in other brain regions of potential relevance, including hippocampus (HIPP) and primary visual cortex (occipital pole) in order to determine ideal regions of interest for future intervention studies.

*Specific Aim 3:* Determine the interrelationship between PET mGluR5 binding across brain regions and symptoms in psychosis disorder patients.

Statistical analysis will be conducted in two phases. The first analysis (i.e., interim analyses, see Power analysis, below) will be conducted following assessment of 10 patients/10 unaffected first-degree relatives, and will provide information to determine whether or not to continue to the second phase of the study. The decision about continuing to phase II will be made by NIMH following review of the phase I data. Of note, the phase I data will be used only for futility analyses to decide on whether or not to proceed with the second study phase.

If the decision is made to proceed to phase II, a second analysis will be conducted using pooled data across the two phases to test the *a priori* hypotheses. Because of the limited sample size and our use of Phase I data solely for the purpose of futility, no statistical correction will be made for the separate analyses conducted following phase I of the study.

Secondary analyses will evaluate group differences in  $BP_{ND}$  at additional ROIs including hippocampus and visual cortex. In exploratory analyses, Pearson’s correlation coefficient (or

Spearman's rho (if data appear non-normal) will be used to investigate relationships between scores on the clinical assessments and BPND within pre-defined brain regions.

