## **Power Analysis**

### **Interim Futility Analysis Plan**

An interim futility analysis will be performed after 10 patients and 10 unaffected first-degree relatives participate in this study. Using the conditional power approach, we have determined the probability that a certain effect size will be found to be significant at the end of the study given the observed effect size at the interim. These probabilities were calculated using simulated data under scenarios matching our design (SAS program available upon request). Assuming a true mean standardized difference (i.e., effect size) of 0.90 between the two groups, if we observe the sample mean standardized difference is less than 0.10 in absolute value between the groups at the midterm (i.e. n=10 in each group), there would be a 23% chance of still finding a significant difference between the groups by the end of study. With an observed midterm difference between 0.10-0.20, 0.20-0.30, or 0.30-0.40 there would be a 30%, 42%, or 50% respectively chance of still detecting a significant difference at the end of study. Thus even with only small differences at the midterm, the chances of still finding a significant result by the end is non-trivial. *Therefore, a cutoff for futility would occur only if the between group effect size is <.10 at the time of mid-point analysis.* Nevertheless, other factors including feasibility and data distribution will be considered and NIMH will have unilateral authority over whether to proceed to phase 2 of the study based upon the results of the interim futility analysis. Screen fails and withdrawals prior to PET scanning will be replaced so the number of evaluable subjects will be reduced only by failure to obtain adequate PET data.

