### **Final Analysis Plan**

This sample size is justified by prior *in vivo* human studies that have found significant differences in mGluR5 PET binding with similar sample sizes: 10-23% reductions were detected between depressed patients (n=11) versus healthy (n=11), 5% reductions between sleep deprived versus non-sleep deprived periods in a within person design (n=22). These reductions translate to effect sizes (by scaling the standard errors by sample sizes) of 0.95-1.2 and 0.90. With the proposed sample size of 20 affected individuals versus 20 unaffected 1st degree relatives, with a two-sided alpha level equal to 0.05, we have >80% power to detect effect size differences of 0.90. Assuming the affected versus unaffected differences in mGluR5 PET binding are at least as large as those found due to depression or sleep, we will have >80% power to detect it. For the exploratory aim, we will be able to detect correlations of 0.35 or greater to be statistically significant with alpha = 0.05 and >80% power.

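### The primary two-sample t-test treats carriers and their own relatives as independent, so its error rate is right only if family correlation is zero or the family layout happens to cancel it

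*SAP*

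**What the plan says.** The opening section of the SAP defines the study as a comparison of "mutation carriers and their unaffected first-degree relatives", with 20 people per group. For Specific Aim 1 it fixes the method: "Two-sample t-tests will be used to test for the global effects of" the mutation, with regional binding potential "in DLPFC as the primary outcome variable". The interim look comes "following assessment of 10 patients/10 unaffected first-degree relatives", so the same related groups are used there. The plan for other regions is "Secondary analyses will evaluate group differences in" binding potential; no different test is named for them.

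The Final Analysis Plan justifies 20 per group "with a two-sided alpha level equal to 0.05" and an effect size of 0.90. The Interim Futility Analysis Plan says of its conditional-power figures: "These probabilities were calculated using simulated data under scenarios matching our design". It does not say whether relatedness was among those scenarios. It also expects some loss of scans: "the number of evaluable subjects will be reduced only by failure to obtain adequate PET data".

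No section mentions pairing, a family term, a kinship adjustment, cluster-robust errors or a limit on members per family.

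**The concern.** A two-sample t-test takes the variance of the group difference as the sum of two independent mean variances. If members of a family have similar binding, two things break that. Similarity between a carrier and a relative makes the difference less variable than the test assumes. Similarity between two carriers, or between two relatives, of one family makes it more variable. Which effect wins depends on how patients and relatives are spread over families.

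At stake is whether the primary p-value, and those for the secondary regions, mean what they say. If the first effect dominates, the study gives away power that its design has paid for. If the second dominates, the 5% level is exceeded. The choice of primary test is SAP content and is stated here, so a protocol that describes family recruitment would not settle the point.

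**Working it through.** **Inputs from the SAP.** 20 patients and 20 relatives; two-sample t-test; two-sided alpha 0.05; effect size d = 0.90 (SD set to 1); stated power above 80%.

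**Assumed inputs.** Within-family correlation rho from 0 to 0.5, and several family layouts. The SAP gives neither.

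**The plan's own figure.** For independent groups the normal approximation is 0.90 × √(20/2) − 1.96 = 2.846 − 1.96 = 0.886, which gives power of 81.2%. This reproduces the stated figure. The noncentral t with 38 df gives 79.2%. The stated figure thus agrees with an independent-groups calculation.

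**Variance with related groups.** Give each family a shared effect with variance rho and each person a residual with variance 1 − rho. A family with a patients and u relatives contributes (a − u) times its family effect to the difference in totals. Let S be the sum over families of (a − u)². Then

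Var(difference) = [rho × S + 40 × (1 − rho)] / 400 = (2/20) × [1 − rho + rho × S/40].

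The test assumes about 2/20, so the true variance is roughly (1 − rho + rho × S/40) times what the test uses. This is approximate, because the pooled sample variance shrinks a little when relatives cluster within one group. Examples at rho = 0.3:
- 20 families of 1:1: S = 0, ratio 1 − 0.3 = 0.70.
- Five 3:1 plus five 1:3: S = 10 × 2² = 40, ratio 1.00.
- Four 4:1 plus four 1:4: S = 8 × 3² = 72, ratio 0.70 + 0.3 × 1.8 = 1.24.

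**True alpha of the planned t-test, by simulation (nominal 5%).** Runs differ from one another by up to about 0.3 points.

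| Assumed layout | S | rho 0.1 | 0.2 | 0.3 | 0.5 |
|---|---|---|---|---|---|
| 20 families of 1:1 | 0 | 3.9% | 3.0% | 2.1% | 0.8% |
| 5 families of 4:4 | 0 | 4.1% | 3.4% | 2.6% | 1.4% |
| Five 3:1 plus five 1:3 | 40 | 5.1% | 5.3% | 5.2% | 5.3% |
| Four 4:1 plus four 1:4 | 72 | 5.9% | 7.0% | 8.3% | 10.8% |

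**Power at d = 0.90 in 1:1 families.** A paired test has noncentrality 0.90 × √(20 / [2(1 − rho)]) on 19 df. At rho = 0.3 this is 0.90 × √14.29 = 3.40, giving 89.7%.

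| Test | rho 0 | 0.1 | 0.2 | 0.3 | 0.5 |
|---|---|---|---|---|---|
| Two-sample t-test | 79% | 80% | 82% | 83% | 87% |
| Paired or family-aware | 77% | 81% | 86% | 90% | 97% |

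At rho = 0.3 a true difference of 0.90 is missed in 17% of studies instead of 10%.

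**If scans fail.** Suppose two scans fail in each group, all in different 1:1 pairs. Power at rho 0.1/0.2/0.3 is 75.6/76.5/77.8% for the t-test, 70.8/75.8/81.1% for a paired test on the 16 complete pairs, and 75.9/80.2/84.9% for a family model on all 36 scans.

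**The case against.** The strongest reply is that in the layout the SAP's wording most readily suggests, with patients matched by relatives in equal totals, the t-test errs on the safe side. Alpha stays at or below 5%, and power is 79–87%, no lower than the 79.2% of an independent 20/20 design. What is lost is power that could have been had: about 4 points at a correlation of 0.2 and 6–7 at 0.3. At 0.1 or below there is nothing material to recover, and at zero a family-aware test is slightly worse. Nothing in the SAP points to a lopsided layout. All of this stands, and it limits the severity.

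Three stronger readings are tempting, and the SAP supports none of them:
- A reader might infer that relatedness inflates the false-positive rate as such. In balanced families it lowers it.
- A reader might infer that drawing the relatives from a few families is enough to push alpha above 5%. Five families of 4:4 give S = 0 and an alpha of 1.4–4.1%. Imbalance within families drives inflation, not a small number of families.
- A reader might infer that the power statement in the Final Analysis Plan fails for this reason. In balanced families it is not undercut.

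It can also be said that a mixed model with one family covariance is itself a simplification, since first-degree relatives include parents, siblings and children, and that it does not win everywhere. In the 3:1 and 1:3 layout its power at correlations of 0 and 0.1 is 76.9% and 78.5%, against 79.2% and 79.4% for the t-test. With all 20 relatives from five 1:4 families plus 15 single patients, it still runs at 5.4–5.8%. That argues against prescribing one exact model, but not for a test that ignores a relationship built into the design.

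**Conclusion.** Wrong as written, and a modest should-fix. The mismatch between an independence test and deliberately related groups is plain from the SAP, and confidence in it is high. Confidence in its size is medium, because the correlation and the layout are both assumed. The test is conservative when S is well below 40, about nominal near 40 and anti-conservative above it. Over the correlations of 0.1 to 0.5 examined, true alpha runs from about 0.8% (1:1 families) to about 10.8% (the S = 72 layout), both at 0.5. These are illustrations, not bounds or estimates for this trial. Nothing here shows that the trial is invalid or that a positive result would be spurious.

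**What to change.** Prespecify a family-aware primary analysis of DLPFC binding. One suitable form is a linear mixed model on all evaluable scans, with group as fixed effect, a family covariance term and a small-sample degrees-of-freedom correction. Let the family covariance go negative: in 1:1 families, truncating it at zero gave a simulated alpha of 5.8–6.1% at zero correlation and 5.5–5.7% at 0.1, against 4.9% untruncated. A paired t-test is equivalent if every family is 1:1 and complete; otherwise it discards the partner of each failed scan. Use the same approach for the secondary regional group comparisons, keep the two-sample t-test as a sensitivity analysis, and report the family layout with the results.

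The cost is SAP wording and a family identifier in the analysis data; no extra participants or scans are needed. If the correlation is in fact zero, power in 1:1 families falls by about 2 points (79% to 77%). If the final test changes, the conditional-power figures in the Interim Futility Analysis Plan need re-running, with the assumed relatedness stated.

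### The SAP does not fix who enters the Aim 3 symptom correlation; its detectable r of 0.35 cannot be significant in 20 patients, and an unadjusted correlation across both groups would be confounded by group

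*SAP*

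**What the plan says.** The design is to "enroll 40 individuals (20 affected with the mutation and 20 unaffected"), the latter being first-degree relatives. Specific Aim 3 is to "Determine the interrelationship between PET mGluR5 binding across brain regions and symptoms in psychosis disorder patients".

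The only analysis that serves this aim is the exploratory one closing the section before Power Analysis. A Pearson coefficient, or Spearman's rho if the data look non-normal, "will be used to investigate relationships between scores on the clinical assessments and BP ND within pre-defined brain regions". The sentence does not say whether patients, relatives or both are included, and it has no group term or stratification.

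The Final Analysis Plan adds, for the exploratory aim, that "we will be able to detect correlations of 0.35 or greater to be statistically significant", and completes the claim as "statistically significant with alpha = 0.05 and >80% power". No sample size or sidedness is attached to it. For the group comparison, the same section works "with a two-sided alpha level equal to 0.05" and says "we have >80% power to detect effect size differences of 0.90".

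**The concern.** The aim names patients, the analysis names nobody, and the power figure does not fit 20 patients. An analyst could therefore run the correlation in 20 patients or in all 40 people, and these answer different questions.

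In patients alone, the coefficient measures whether those with more symptoms have higher or lower binding. Across both groups without adjustment, it also carries the difference between affected and unaffected people. If the groups differ in binding, as the design assumes, and also in symptom scores, the coefficient is non-zero even when symptoms and binding are unrelated inside each group. A result reported for Aim 3 could then be the Aim 1 group difference in another form. Separately, the stated sensitivity of the exploratory aim would mislead a reader under either choice of population.

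**Working it through.** **Inputs from the SAP.** 20 affected and 20 unaffected; design difference in binding d = 0.90, with prior effect sizes of 0.95 to 1.2 also cited; target r = 0.35; alpha 0.05; power above 80%. The correlation sentence gives no sidedness. I use two-sided, as in the group comparison, and show one-sided as a check.

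**Assumptions.** The affected group stands for the patients of Aim 3. No scans are lost. Data are normal within group. The SAP gives no symptom distribution, so the separation s between groups (in within-group SDs) is varied.

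**1. The group-comparison power.** For d = 0.90 and 20 per group, two-sided 0.05, the normal approximation gives 81.2% and the noncentral t gives 79.2%. That figure reproduces to within about a point of 80%, so the conventions used here are close to the plan's.

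**2. The correlation figure.** Power ≈ Φ(atanh(r)·√(n − 3) − z), with atanh(0.35) = 0.365 and z = 1.96.

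- n = 20: 0.365 × √17 − 1.96 = −0.45, power 33% (simulation 34%).
- n = 40: 0.365 × √37 − 1.96 = 0.26, power 60% (simulation 61%).
- One-sided: 45–46% at n = 20 and 72–73% at n = 40.

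The n needed for 80% power at r = 0.35 is (2.80/0.365)² + 3, about 62 two-sided, or 50 one-sided. The stated power is not reproduced for either population.

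**3. Smallest significant r.** r = t/√(n − 2 + t²).

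- n = 20: t = 2.101, r = 2.101/√(18 + 4.414) = 0.444 (one-sided 0.378).
- n = 40: t = 2.024, r = 2.024/√(38 + 4.098) = 0.312.

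An observed 0.35 is not significant in 20 patients, even one-sided. It passes the threshold only in all 40.

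**4. Correlation detectable with 80% power, two-sided.** r = tanh(2.80/√(n − 3)): tanh(2.80/√17) = 0.59 at n = 20; tanh(2.80/√37) = 0.43 at n = 40. With adjustment for group, n − 4 replaces n − 3: tanh(2.80/√36) = 0.44.

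**5. Correlation due to group alone.** With equal groups and no within-group relation, the expected correlation across all 40 is [d/√(d² + 4)]·[s/√(s² + 4)]. At d = 0.90 the first factor is 0.9/√4.81 = 0.410. The share of trials with a significant result comes from simulation (at least 40,000 trials per cell):

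| s (SD) | Second factor | Expected r | Significant at 0.05 |
|---|---|---|---|
| 1 | 0.447 | 0.18 | 21% |
| 2 | 0.707 | 0.29 | 47% |
| 3 | 0.832 | 0.34 | 62% |
| 4 | 0.894 | 0.37 | 69% |

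The nominal rate is 5%. As a check, a symptom score that merely labels the group gives r = 0.41 and 79% significant, which is the t-test power in step 1.

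**6. Sensitivity to d.** At d = 0.45, separations of 2, 3 and 4 SD give 16%, 21% and 23%. At d = 1.2 they give 69%, 84% and 90%.

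**7. Does adjustment work?** With group-centred values and 37 degrees of freedom, at d = 0.90 and s = 3, the mean r was 0 and 5.0% of trials were significant.

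**The case against.** The strongest reply is that Aim 3 already names patients and the exploratory sentence should be read with it. The SAP nowhere says the two groups are combined for this analysis; its one mention of pooling concerns the two study phases. This stands, and it limits the point to an unresolved conflict in the text.

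A reader might infer from 0.35 that the authors meant all 40. The documents do not support that. The figure clears the significance threshold at 40 but misses the claimed power there too (60%), and a figure that is wrong for both sample sizes cannot show which was used.

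A reader might also infer that the planned group difference alone yields r = 0.35. At d = 0.90 this needs a symptom separation of about 3.3 SD (about 2.8 SD at 0.95 and 1.9 SD at 1.2). The SAP gives no symptom scores and defines the groups by mutation status, not by symptom extremes. The inflation at 1 SD, where r is only 0.18, shows that the problem does not depend on reaching 0.35.

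The SAP also does not say who receives the clinical assessments, which the protocol may settle. If only patients are rated, a correlation across both groups cannot arise. The conflict with the power sentence would remain.

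Finally, these analyses are labelled exploratory. They do not touch the primary DLPFC comparison, the futility rule or the power of the group comparison.

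**Conclusion.** The point holds as a conflict within the SAP. The aim specifies patients, the analysis sentence leaves population and group adjustment open, and the power sentence calls significant a correlation that cannot be so in 20 patients. The power claim is wrong under either reading: about 33% at n = 20 and 60% at n = 40, two-sided.

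The confounding is conditional on an unadjusted analysis of all 40, which the SAP does not state. Under that condition, with d = 0.90 and no within-group relation, false positives run from 21% to 69% over assumed symptom separations of 1 to 4 SD.

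It would be too strong to say that a positive Aim 1 makes Aim 3 positive automatically: even at 4 SD about three trials in ten would not be significant, and at d = 0.45 most would not be. The wording should be corrected because Aim 3 is a numbered aim and the correction is small, but the primary result is not at risk.

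**What to change.** In the exploratory-analysis sentence, state one of the following:

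- the Aim 3 correlations are computed within the CNTNAP2 patients only, which matches the aim; or
- all 40 participants are used, with a partial correlation adjusted for group (or group-centred values).

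Add that an unadjusted correlation across both groups will not be reported as evidence for Aim 3.

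In the Final Analysis Plan, replace 0.35 with the correlation detectable at 80% power, two-sided 0.05, in the chosen population, and give the n: about 0.59 for 20 patients, or about 0.43 for 40 (0.44 after allowing for the group term).

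The cost is a few sentences. Patients only means wider intervals; adjustment in all 40 loses one degree of freedom and estimates a within-group relation assumed common to patients and relatives. Either way the stated sensitivity becomes less favourable.

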## **Power Analysis**

### **Interim Futility Analysis Plan**

An interim futility analysis will be performed after 10 patients and 10 unaffected first-degree relatives participate in this study. Using the conditional power approach, we have determined the probability that a certain effect size will be found to be significant at the end of the study given the observed effect size at the interim. These probabilities were calculated using simulated data under scenarios matching our design (SAS program available upon request). Assuming a true mean standardized difference (i.e., effect size) of 0.90 between the two groups, if we observe the sample mean standardized difference is less than 0.10 in absolute value between the groups at the midterm (i.e. n=10 in each group), there would be a 23% chance of still finding a significant difference between the groups by the end of study. With an observed midterm difference between 0.10-0.20, 0.20-0.30, or 0.30-0.40 there would be a 30%, 42%, or 50% respectively chance of still detecting a significant difference at the end of study. Thus even with only small differences at the midterm, the chances of still finding a significant result by the end is non-trivial. *Therefore, a cutoff for futility would occur only if the between group effect size is <.10 at the time of mid-point analysis.* Nevertheless, other factors including feasibility and data distribution will be considered and NIMH will have unilateral authority over whether to proceed to phase 2 of the study based upon the results of the interim futility analysis. Screen fails and withdrawals prior to PET scanning will be replaced so the number of evaluable subjects will be reduced only by failure to obtain adequate PET data.

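### The conditional powers of 23/30/42/50% and the final power above 80% are higher than the planned t-test gives (about 18/25/34/45% and 79.2%)

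*SAP*

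**What the plan says.** The primary analysis in the SAP is a two-sided comparison of the two groups: "Two-sample t-tests will be used to test for the global effects", with DLPFC binding potential as the outcome. If the study continues, the final test pools both phases.

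Under Interim Futility Analysis Plan, the interim look comes at 10 per group and the true effect is taken as 0.90. The SAP states: "These probabilities were calculated using simulated data under scenarios matching our design". The first band is an observed standardized difference "less than 0.10 in absolute value between the groups at the midterm", for which "there would be a 23% chance of still finding a significant difference between the groups by the end of study". The sentence after it reads "With an observed midterm difference between 0.10-0.20, 0.20-0.30, or 0.30-0.40 there would be a 30%, 42%, or 50" per cent, in that order. The SAP concludes "Thus even with only small differences at the midterm, the chances of still finding a significant result by the end is non-trivial", and on that ground places the futility cutoff at 0.10. Neither the number of replicates nor the test coded in the simulation is given; the SAS program is offered on request.

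Under Final Analysis Plan, with 20 per group and two-sided alpha 0.05, the SAP says "we have >80% power to detect effect size differences of 0.90".

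**The concern.** The SAP supplies everything needed to repeat the first-band calculation: test, sidedness, alpha, both sample sizes, the true effect, and the band. Repeating it with the planned t-test gives a clearly lower figure than the one printed. If the first band's definition is read across to the other three, they are lower too, in the same direction.

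The four percentages are the SAP's only quantitative argument for putting the cutoff at 0.10, and they bear on the sponsor's decision whether to continue to phase II. The final power statement is an inequality, and it fails by a small margin for the test that will be used. What is at stake is the accuracy of the stated operating characteristics, not a decision rule.

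**Working it through.** **Inputs, all from the SAP.** True standardized difference 0.90 (SD set to 1); interim 10 per group; final pooled 20 per group; two-sided alpha 0.05; two-sample t-test; first band on the absolute standardized difference, read across to the other bands.

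**1. Reproducing the printed figures.** With known variance, the interim difference m has variance 2/10 = 0.20. The final difference is the average of the two phases, so given m it has mean (m + 0.90)/2 and variance 0.20/4 = 0.05. The final z-test rejects above 1.96 × √0.10 = 0.620; the lower tail is negligible. Hence

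conditional power = Φ{[(m + 0.90)/2 − 0.620] / √0.05}.

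At m = 0 this is Φ(−0.76) = 22.4%. Over the whole band, simulation with the z-test (10,000,000 trials, absolute standardized bands) gives 23.6%, 30.1%, 39.9% and 50.5%. That is close to the printed 23%, 30%, 42% and 50%; the third band is about 2 points off.

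**2. The planned test.** The same design with the pooled t-test (38 degrees of freedom), 40,000,000 trials:

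| Band | SAP | t-test, absolute standardized | t-test, absolute raw | t-test, signed raw | z-test, absolute standardized |
|---|---|---|---|---|---|
| below 0.10 | 23% | 18.4% | 19.5% | 22.2% | 23.6% |
| 0.10–0.20 | 30% | 24.7% | 26.1% | 30.4% | 30.1% |
| 0.20–0.30 | 42% | 34.5% | 36.2% | 39.4% | 39.9% |
| 0.30–0.40 | 50% | 45.3% | 46.8% | 48.7% | 50.5% |

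On absolute standardized bands the printed values exceed the t-test by 4.6, 5.3, 7.5 and 4.7 points. Separate runs with other seeds agree to within about 0.3 points. Welch's version gives 18.3%, 24.4%, 34.4% and 44.9%.

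**3. Could simulation error account for it?** Only about 2.4% of simulated trials fall in the first band, so the standard error of that figure is √[0.184 × 0.816 / (0.024 × N)] for N replicates: about 8 points at N = 1,000 and 2.5 points at N = 10,000. The replicate count is not stated, so these values of N are assumptions.

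| N (assumed) | First band alone, p | All four bands jointly (chi-square, 4 df), p |
|---|---|---|
| 1,000 | 0.56 | 0.74 |
| 5,000 | 0.20 | 0.04 |
| 10,000 | 0.07 | 0.0004 |

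These compare the printed values with the t-test on absolute standardized bands. Noise is a natural explanation with a thousand or so replicates and a poor one at 10,000.

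**4. Final power.** The noncentrality is 0.90 × √(20/2) = 2.846.

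- Normal approximation: Φ(2.846 − 1.960) = Φ(0.886) = 81.2%.
- Noncentral t, 38 degrees of freedom: 79.2%.
- The t-test reaches 80% at 20 per group when the effect size is 0.909, or at 0.90 with 21 per group (81.2%).
- The SAP allows that "the number of evaluable subjects will be reduced only by failure to obtain adequate PET data"; at 19 per group the power would be 77.0%.

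**The case against.** **The cause cannot be settled without the program.** The z-test fits, but so does the planned t-test with signed bands on the raw difference (joint p about 0.87 at an assumed 10,000 replicates), and so does the t-test as described with one or two thousand replicates. A reader might infer that the sponsor simulated the wrong test, all the more because a known-variance calculation would also yield the power claim above 80%. The SAP does not say so and the figures do not prove it. This part of the objection stands in full. It does not rescue the printed numbers: signed bands would contradict the SAP's own wording for the first band, and a figure that is off through too few replicates still needs replacing.

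**The other bands are defined.** A reader might also say that bands two to four cannot be checked because the absolute value is not repeated for them. The SAP prints their limits, and the sentence before supplies both the standardized scale and the absolute value. They can be checked, and on that natural reading they show the same excess as the first band.

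**Nothing turns on it.** This stands as well. An 18% chance is still not trivial, a lower figure makes stopping below 0.10 slightly easier to defend, and the sponsor keeps sole authority over continuation. A reader might infer that the cutoff is undermined; the figures do not support that. The shortfall in final power is under one point, and the effect size of 0.90 is itself an approximate value taken from earlier studies.

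**Conclusion.** The point holds and is minor. For the two-sided t-test that the SAP plans, the conditional powers are about 18%, 25%, 34% and 45%, against the stated 23%, 30%, 42% and 50%. In the first band, which carries the cutoff, the stated chance is about a quarter too high in relative terms (23/18.4 = 1.25). Final power at 0.90 with 20 per group is 79.2%, so the claim of more than 80% is false for that test by 0.8 points.

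This rests on normally distributed data with equal variances, all 20 per group evaluable, and the first band's absolute standardized definition applied to all four bands. Whether the excess comes from a known-variance calculation, a different coding of the bands or a small number of replicates is not established.

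**What to change.** Re-run the existing simulation with the planned two-sample t-test, absolute standardized bands throughout and about 100,000 replicates (standard error about 0.8 points per band), and state the replicate count. Replace the four percentages with the result, expected to be about 18%, 25%, 34% and 45%. If the present figures prove to be a known-variance approximation, they may instead be kept and labelled as such. Under Final Analysis Plan, restate the power as about 79% at an effect size of 0.90 with 20 evaluable per group, reaching 80% at 0.91.

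The cost is one program run and a few words in the SAP. The 0.10 cutoff, the test, alpha and the sample size are unchanged; the only loss is that the stated figures become slightly less favourable.
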